4.1 Enrolment/screening period (Visit 1 to Visit 2)

Procedures will be performed according to the Study Plan [Table 1](#).

At enrolment, obtain written informed consent prior to any study procedure or change in medical therapy required by the protocol. Consenting patients are assessed to ensure that they meet eligibility criteria. Patients who do not meet these criteria must not be enrolled in the study.

The below assessments to be performed for all consented patients at Visit 1:

- Contact IVRS/IWRS to obtain unique patient enrolment number
- Review and confirm the patient's eligibility for the study by assessing inclusion and exclusion criteria listed in Sections [3.1](#) and [3.2](#).
- A standard patient medical, medication and surgical history will be obtained with the review of selection criteria
- Record demography (including sex, age, race and ethnic group)
- Perform brief physical examination
- Obtain vital signs (seated BP and pulse), body weight and height
- Obtain specimen (blood) for HbA1c
- Obtain specimens (blood) for S-Creatinine for eGFR calculation
- Perform urine pregnancy test for women of child bearing potential. Serum pregnancy test (β hCG) is performed, if urine pregnancy test result is positive
- Review concomitant medications
- Schedule the entry into lead-in visit between 06.00 a.m. and 10.00 a.m.
- Remind patient to be fasting and withhold anti-diabetic medications, insulin, anti-hypertensive drugs, lipid lowering drugs and anti-platelet drugs, the morning of their next visit and to refrain from tobacco/nicotine for 12 hours and alcohol for 24 hours, respectively prior to next visit

4.2 Single-blind placebo lead-in period (Visit 2 to Visit 4)

4.2.1 Visit 2, Start of lead-in

At visit 2 patients will be examined for HbA1c and eGFR level from blood sample obtained from Visit 1. If the HbA1c ≥ 7.0 and $\leq 11.0\%$ and the eGFR value is within the range 40-65 mL/min/1.73 m² (MDRD-formula), then patients will enter a 4-week single-blind placebo

lead-in period. At the lead-in visit, the patient's current dietary and life-style will be reviewed. Patients will be instructed on diet and life-style in accordance with the local Diabetes guidelines or ADA guidelines by a qualified member of the study staff beginning with the lead-in visit. The below procedures will be performed during the visit for the eligible patients:

- Review and confirm the patient's eligibility for the study by assessing inclusion and exclusion criteria listed in Sections 3.1 and 3.2.
- Perform complete physical examination and body weight
- Obtain vital signs (seated BP and pulse)
- Perform 12-lead ECG. ECG must be obtained and reviewed with no significant abnormalities prior to Randomization
- Obtain specimens (blood) for hepatitis screen panel, safety laboratory panel including S-Creatinine for eGFR calculation, CCI [REDACTED]
- Perform urine pregnancy test for women of child bearing potential. Serum pregnancy test (β hCG) is performed, if urine pregnancy test result is positive
- Obtain specimen for urinalysis (dip stick and spot urine collection)
- Contact IVRS/IWRS to register visit and obtain study drug dispensing bottle assignment number and dispense study drug bottle
- Have patient to take their first dose of lead-in period study drug
- Provide instruction on diet and life-style
- Dispense blood glucose meter and supplies, provide instruction on their use and self-monitoring of blood glucose (see Section 5.2.5.1)
- Provide instruction on recording daily insulin doses and glucose values (when symptoms suggestive of hypoglycaemia) in the patient diary
- Remind patient to be fasting and withhold study drug and other anti-diabetic medications, insulin, anti-hypertensive drugs, lipid lowering drugs and anti-platelet drugs, the morning of their next visit and to refrain from tobacco/nicotine for 12 hours and alcohol for 24 hours, respectively prior to next visit
- Remind patient to bring study drug, diary and glucose meter to the next scheduled visit
- Review concomitant medications and SAEs from Visit 1.

4.2.2 Visit 3, Lead-in

- Obtain vital signs (seated BP and pulse) and body weight
- Obtain specimens (blood) for S-Creatinine for eGFR calculation
- Perform urine pregnancy test for women of child bearing potential. Serum pregnancy test (β hCG) is performed, if urine pregnancy test result is positive
- Dispense blood glucose meter supplies and diary (if required)
- Review diary and calculate mean total daily dose of insulin (see Section 5.1.8)
- Review concomitant medications
- Assess AEs including hypoglycemic events (see Section 6.3.7)
- Remind patient to be fasting and withhold study drug and other anti-diabetic medications, insulin, anti-hypertensive drugs, lipid lowering drugs and anti-platelet drugs, the morning of their next visit and to refrain from tobacco/nicotine for 12 hours and alcohol for 24 hours, respectively prior to next visit

4.3 Treatment period

Descriptions of the procedures for this period are included in the Study Plan Table 1. The specific requirements for the treatment period are mentioned below:

4.3.1 Visit 4, Randomization

At Visit 4, patients who meet all of the inclusion and none of the exclusion criteria, including the eGFR value between 45-59 mL/min/1.73 m² at Visit 1, or Visit 2, or Visit 3 - will be randomized to the 24 weeks double-blind treatment period.

- Perform brief physical examination
- Measure body weight and CCI
- Obtain vital signs (seated and orthostatic BP and pulse)
- Obtain specimen (blood) for safety laboratory panel including S-Creatinine for eGFR calculation

CCI

- Perform urine pregnancy test for women of child bearing potential. Serum pregnancy test (β hCG) is performed, if urine pregnancy test result is positive

- Obtain specimen for urinalysis (dip stick and spot urine collection)
- Timed urine sample collection (24-hours) (see Section 5.1)
- Contact IVRS/IWRS to randomize patient and obtain study drug dispensing bottle assignment number and dispense the study drug bottle
- Patient will be administered his/her first dose of the double-blind treatment at site
- Provide dietary and life-style advice
- Dispense glucose meter supplies and diary (if required)
- Review diary and calculate mean total daily dose of insulin for baseline (see Section 5.1.8)
- Collect and assess compliance with lead-in period study drug based on tablet count (see Section 7.5)
- Review concomitant medications and AEs including hypoglycemic events
- Remind patient to withhold study drug and other anti-diabetic medications, insulin, anti-hypertensive drugs, lipid lowering drugs and anti-platelet drugs, the morning of their next visit and to refrain from tobacco/nicotine for 12 hours and alcohol for 24 hours, respectively prior to next visit

4.3.2 Visit 5, Treatment

- Measure body weight CCI XXXXXXXXXX
- Obtain vital signs (seated and orthostatic BP and pulse)
- Perform urine pregnancy test for women of child bearing potential. Serum pregnancy test (β hCG) is performed, if urine pregnancy test result is positive
- Dispense glucose meter supplies and diary (if required)
- Review diary and calculate mean total daily dose of insulin (see Section 5.1.8)
- Review concomitant medications and AEs including hypoglycemic events
- Remind patient to be fasting and withhold study drug and other anti-diabetic medications, insulin, anti-hypertensive drugs, lipid lowering drugs and anti-platelet drugs, the morning of their next visit and to refrain from tobacco/nicotine for 12 hours and alcohol for 24 hours, respectively prior to next visit

4.3.3 Visit 6, Treatment

- Perform brief physical examination
- Measure body weight and **CCI**
- Obtain vital signs (seated and orthostatic BP and pulse)
- Obtain specimens (blood) for safety laboratory panel including S-Creatinine for eGFR calculation
- Obtain specimen (blood) for HbA1c and FPG
- Assess FPG for rescue (see Section 4.3.3.1 for details)
- Perform urine pregnancy test for women of child bearing potential. Serum pregnancy test (β hCG) is performed, if urine pregnancy test result is positive
- Obtain specimen for urinalysis (dip stick and spot urine collection)
- Contact IVRS/IWRS and obtain study drug dispensing bottles assignment number and dispense the study drug bottles
- Collect and assess compliance with study drug based on tablet count (see Section 7.5)
- Provide dietary and life-style advice
- Dispense glucose meter supplies and diary (if required)
- Review diary and calculate mean total daily dose of insulin (see Section 5.1.8)
- Review concomitant medications and AEs including hypoglycemic events
- Remind patient to be fasting and withhold study drug and other anti-diabetic medications, insulin, anti-hypertensive drugs, lipid lowering drugs and anti-platelet drugs, the morning of their next visit and to refrain from tobacco/nicotine for 12 hours and alcohol for 24 hours, respectively prior to next visit

4.3.3.1 Rescue Medication Due to Lack of Glycemic Control in the Treatment Period

Patients with lack of glycemic control during the 24-week treatment period may be eligible to receive open-label rescue medication in addition to their blinded treatment in order to treat ongoing hyperglycemia. Patients may receive open-label rescue medication added on to, but not as a replacement for, their current study drug regimen. Rescue medication in this protocol refers to any approved, appropriate anti-diabetic agent, except SGLT2-inhibitors, for which there is either initiation or upward titration, in accordance with the approved label and

conventional standards of care. Open-label rescue medication is to be titrated as needed to obtain adequate glycemic control. Patients who received a first rescue medication, who subsequently fulfil lack of glycemic control criteria, may have other rescue medications added or substituted, according to Investigator judgment.

During the 24-week double-blind treatment period, all rescue decisions will be based on central laboratory FPG and confirmatory FPG results. If patients meet the protocol-specified glycemic criteria based on FPG, they will be recommended for open-label rescue medication.

Between scheduled visits, the patients will be asked to check their blood glucose if they develop symptoms suggestive of hyperglycemia. The sections and tables listed below define the lack of glycemic control criteria. Glucometers will be provided by AstraZeneca. The patients will receive instructions for the use of the glucometer according to the manufacturer's instructions. Patients will be instructed to contact the investigator if they experience a hyperglycemic event in order to schedule an extra visit for central laboratory FPG and if needed, a confirmatory, repeat FPG.

Patients in the follow-up phase will not need to adhere to the protocol defined rescue criteria, and may have their anti-diabetic regimen adjusted at the Investigator's discretion.

The sections and tables listed below define the lack of glycemic control criteria for initiation of open-label rescue medication.

Protocol-Defined Lack of Glycemic Control Criteria for Initiation of Open-Label Rescue Medication

Pre-specified glycemic criteria (see [Table 2](#) below), based upon central laboratory FPG and confirmatory, repeat FPG, have been established during the 24-week double-blind treatment period, from Week 4 and up to Week 24 visits, to determine eligibility for open-label rescue medication initiation/titration.

Table 2 **Lack of Glycemic Control Criteria for Initiation of Open-Label Rescue Medication**

Visit Label	Central Laboratory FPG
From Week 4 (Visit 6) to Week 12 (Visit 7) (excluding Week 12)	FPG >240 mg/dL (13.3 mmol/L)
From Week 12 (Visit 7) to Week 24 (Visit 8) (excluding Week 24)	FPG >200 mg/dL (11.1 mmol/L)

Patients with a central laboratory FPG value meeting the lack of glycemic control criterion at a pre-specified visit will be scheduled for a follow-up visit (within 3 - 5 days) to obtain a second central laboratory FPG value and review the patient's glucose meter readings. If the repeat central laboratory FPG value still meets the criterion, the patient will receive rescue medication.

Irrespective of study visit number, patients who meet rescue criteria in the treatment period must first complete the Week 24 visit procedures before receipt of open-label anti-diabetic rescue medication to ensure that important study endpoint measurements are collected.

Following completion of the Week 24 “Rescue” visit, rescued patients will be administered open-label rescue medication in addition to their blinded study drug. Rescued patients will then continue in the treatment period according to their original visit schedule. Patients who received a first open-label anti-diabetic rescue medication, who subsequently fulfill lack of glycemic control criteria described in the [Table 2](#) above, may have other rescue medications added or substituted, according to Investigator judgment, without repetition of rescue visits.

Patients with a central laboratory FPG value >200 mg/dL (11.1 mmol/L) at Week 24 (Visit 8), will not be considered as rescued for efficacy analysis.

Guidelines with regard to changes in insulin dose

Each patient’s baseline insulin therapy should remain unchanged wherever possible throughout the double-blind treatment period. The stable insulin regimen aims to continue insulin as it was being used by the patient at enrollment and lead-in, with no changes to insulin type and with as few changes in insulin dosage as possible. A stable insulin regimen is pivotal, because it makes it possible for the study to measure any differences in glycemic control between the dapagliflozin treatment arm and the matching placebo arm. Down-titration of insulin will be allowed only as necessary to prevent low blood glucose or hypoglycemia. During the double-blind treatment period, a few patients will experience poor glycemic control, as measured by increased FPG measurements from the central laboratory during study visits. When glucose measurements exceed certain limits (as specified in [Table 2](#) above), the patient will be “rescued”.

During the double-blind treatment period, if up-titration of insulin dose is $>10\%$ (lasting more than 7 consecutive days) in comparison to the mean daily insulin dose at baseline, the patient shall be handled as administration of anti-diabetic rescue medication (i.e., the patient must complete the Week 24 visit procedures, as outlined in section [4.3.5](#)) and the patient will continue in the treatment period according to their original visit schedule. Patients must record the daily dose of insulin in the diary provided (minimum of 80% of days with a value) and review any changes in insulin doses with their investigator, either at regularly scheduled visits, or via telephone calls between visits. Patients required to be rescued, shall be called for an unscheduled visit within 5 days, to complete the Week 24 procedures.

Any insulin dose changes (even if more than $\pm 10\%$ of the mean daily insulin dose at baseline) is not considered as an up or down titration as long the insulin dose change is not for a period of more than 7 consecutive days. For example, dose changes due to known changes in physical activity or food intake will not be registered as up or down titration as long as the insulin dose is back to the previous dose after the change. Similarly, if insulin requirement has increased temporarily, e.g., due to an infection, it will not be considered an up-titration even if the insulin dose increase is more than 10% of the baseline mean daily insulin dose, as

long as such an increase is for a period of not more than 7 consecutive days and the insulin dose is expected to return to the baseline level once the precipitating condition has resolved.

4.3.4 Visit 7, Treatment

Perform the same assessments as detailed in visit 6 (see Section 4.3.3).

4.3.5 Visit 8, End of Treatment/Discontinuation/Rescue

Randomized patients discontinuing study drug or requiring rescue should have Visit 8 (Week 24) procedures done at the time of rescue or study drug discontinuation. All patients who discontinue study drug will be asked to continue ordinary visit schedule, unless they entirely withdraw consent from the study.

- Perform complete physical examination
- Measure body weight CCI
- Obtain vital signs (seated and orthostatic BP and pulse)
- Obtain specimen (blood) for safety laboratory panel including S-Creatinine for eGFR calculation

CCI

- Perform urine pregnancy test for women of child bearing potential. Serum pregnancy test (β hCG) is performed, if urine pregnancy test result is positive
- Obtain specimen for urinalysis (dip stick and spot urine collection)
- Timed urine sample collection (24-hours) (see Section 5.1)
- Collect and assess compliance with study drug based on tablet count
- Provide dietary and life-style advice
- Dispense glucose meter supplies and diary (if required)
- Review diary and calculate mean total daily dose of insulin
- Review concomitant medications and AEs including hypoglycemic events
- Remind patient to be fasting and withhold anti-diabetic medications, insulin, anti-hypertensive drugs, lipid lowering drugs and anti-platelet drugs, the morning of their next visit and to refrain from tobacco/nicotine for 12 hours and alcohol for 24 hours, respectively prior to next visit

4.4 Follow-up period, Visit 9

Descriptions of the procedures for this period are included in the Study Plan [Table 1](#). The specific requirements for the follow up period are mentioned below:

After completion of Week 24 visit, patients will enter a 3-week safety follow-up period without study drug. The follow-up visit (Visit 9) provides the opportunity to further evaluate changes in physical signs, renal function (i.e., changes in eGFR), symptoms or laboratory parameters that may be related to dapagliflozin.

- Perform brief physical examination
- Measure body weight
- Obtain vital signs (seated and orthostatic BP and pulse)
- Obtain specimen (blood) for safety laboratory panel including S-Creatinine for eGFR calculation

CCI

- Perform urine pregnancy test for women of child bearing potential. Serum pregnancy test (β hCG) is performed, if urine pregnancy test result is positive
- Obtain specimen for urinalysis (dip stick and spot urine collection)
- Review diary and calculate mean total daily dose of insulin
- Review concomitant medications and AEs including hypoglycemic events

5. STUDY ASSESSMENTS

The Rave[®] Web Based Data Capture (WBDC) system will be used for data collection and query handling.

The investigator will ensure that data on the observations, tests, and assessments specified in the protocol are recorded on the eCRF provided by AstraZeneca as specified in the study protocol and in accordance with the instructions provided. The CRF will be accompanied with “Instructions for the investigator”, which should be followed. These instructions provide guidance for the recording of study data in the CRF including how to change data incorrectly recorded.

The investigator will ensure that data are recorded on the eCRF as specified in the study protocol and in accordance with the instructions provided.

The investigator ensures the accuracy, completeness, and timeliness of the data recorded and of the provision of answers to data queries according to the Clinical Study Agreement (CSA). The investigator will sign the completed eCRF. A copy of the completed eCRF will be archived at the study site.

5.1 Efficacy assessments

Blood and urine samples will be obtained at specified time points for laboratory evaluations. The central laboratory for this study will perform the analysis of all scheduled laboratory tests and will provide reference ranges for these tests. The detailed methods for specimen collection, handling, processing, shipping, and storage will be supplied in the Investigator's Laboratory Manual provided by the Central Laboratory. All clinical laboratory tests will be performed by the Central Laboratory or designated reference laboratory.

During the double-blind treatment period, HbA1c and urinary glucose values will be blinded to the Investigator and to the Sponsor. These values will be provided to the Investigator after the study has been completed. FPG value will be reported as an un-blinded value throughout the study.

All glycemic efficacy objectives will be based on values measured by central laboratory. Any self-monitored blood glucose measured by the patient and FPG measured by the site using glucometer will be used only for safety purposes. [Note: The patients will be asked to check their blood glucose only if they develop symptoms suggestive of hypoglycemia or hyperglycemia and to record hypoglycemia symptoms in the patient diary.]

5.1.1 HbA1c

HbA1c is the primary assessment for the determination of glycemic efficacy and will be analysed by a central laboratory according to the procedures described in the Laboratory Manual which will be distributed to each study site during site initiation.

5.1.2 FPG

FPG is a well established measure of glycemic efficacy and considered to be an acceptable secondary endpoint. FPG will be analysed by a central laboratory according to the procedures described in the Laboratory Manual which will be distributed to each study site during site initiation.

5.1.3 Weight and height

The patient's weight will be recorded in kilogram (kg) to one decimal place, with light clothing and no shoes. All readings should be recorded as accurately as possible and the same scale should be used for all assessments for a given patient. The patient's height will be recorded in centimetres, with no shoes.

5.1.4 BMI

BMI is a calculated ratio between weight and height (weight / height², where weight is measured in kg, and height in metres) and will be computed by AstraZeneca.

5.1.5 Vital signs

5.1.5.1 Seated blood pressure and pulse

Pulse and BP measurements must be taken consistently throughout the study. Pulse and BP should be recorded using the same equipment at each visit. Use only the right or the left arm when measuring these parameters. Document which arm was used, along with the observer's initials. The same arm should be used at all visits for each position. At each study visit, BP and pulse measurements should be obtained prior to blinded study drug administration. Pulse and BP will be measured thrice (1 minute apart) before any blood sampling is done after the patient has been sitting and resting for least 5 minutes. BP readings should be taken while the patient is in a comfortable seated position with the arm supported at the level of the heart. All three readings must be recorded in eCRF. For study analyses, the average of the three BP and pulse readings will be used.

CCI

5.1.8 Insulin dose

The daily insulin dose will be recorded in patient diary by patient and the mean daily dose is calculated by investigator. The calculated mean daily insulin dose is an average daily insulin use from the last visit.

5.1.9 eGFR

eGFR is calculated according to the MDRD formula): $GFR (mL/min/1.73m^2) = 175 \times (\text{standardized sCr})^{-1.154} \times (\text{Age})^{-0.203} \times (0.742 \text{ if female}) \times (1.212 \text{ if Black})$ [Note: sCr reported in mg/dL]

CCI

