	Enrolment		Start of lead-in	Lead-in	Randomization	Treatment	Treatment	Treatment	End of Treatment/Discontinuation/Rescue	Follow-up		
Visit	1^a Non-fasting		2^b Fasting	3^c Fasting	4^{c,d} Fasting	5^{c,d,e} Non-fasting	6^{c,d,e} Fasting	7^{c,d,e} Fasting	8^{c,d,e} Fasting	9 Fasting		
Week	-6		-4	-1	0	1	4	12	24	27		
Day	-42 to -29		-28	-7	1	8	29	85	169	190		
Visit Window			±3	±3	±0	±5	±5	±5	±5	±5		
Urinalysis (dipstick and spot urine collection)			X		X		X	X	X	X		5.2.1
Timed urine sample collection (24-hours)					X				X			5.1.7
Dietary and life-style advice			X		X		X	X	X			4.2.1
Dispense Glucose Meter and/or Supplies (including diaries) /Provide Instructions			X	X	X	X	X	X	X			5.1.8 and 5.2.5.1
Review of diaries				X	X	X	X	X	X	X		5.1.8 and 5.2.5.1
Dispensation of Study Medication via IVRS/IWRS			X		X		X	X				7
Return of Study Medication and accountability					X		X	X	X			7.5 and 7.6
Adverse event review (AEs and SAEs) ⁿ	X		X	X	X	X	X	X	X	X		6
Hypoglycemic events review			X	X	X	X	X	X	X	X		5.2.5.1 and 6.3.7
Concomitant medication	X		X	X	X	X	X	X	X	X		7.7

- ^a Screening procedures, indicated under Visit 1, can be completed over multiple visits, provided all procedures have been completed, with the results reviewed, prior to Visit 2.
- ^b Patients must have their Visit 2 completed within 14 days following Visit 1. Visit window of ± 3 for Visit 2 corresponds to the randomization visit (Visit 4). Note: The single-blind lead-in study medication and the central laboratory results from Visit 1 must have been received at the site prior to completing the entry into Visit 2.
- ^c Central Laboratory samples must be collected in a fasting state (at least 8 hours of fasting prior to the study visit) except visit 5, and patients should be seen between 6 a.m. and 10 a.m. Patients must refrain from tobacco/nicotine for 12 hours and alcohol for 24 hours, respectively prior to study visits. Ensure to collect all fasting blood samples prior to the morning dose(s) of blinded study medication. Doses of study medication and other concomitant medications on the day of the visits must be taken upon completion of study visit procedures. (See Section 3.8)
- ^d Double-blind treatment period visits must be scheduled according to the randomization visit date (Day 1), with a protocol-allowed visit window of ± 5 days. Patients will bring their glucose meter and study supplies to the site at all visits. Any slippage in time from one visit must not accumulate to affect other visits.

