#### 4.3.10 Missing Insulin Dose

For patients who took insulin before or during the study, the mean total insulin dose should be collected in the CRF which includes the dosing values with start and end dosing date. If there are missing dosing values or date gaps during the insulin treatment period, linear interpolation will be used to fill in the missing doses or missing days. The interpolated values will be used to determine if the increase of  $\geq 10\%$  increase in insulin occurred for those patients.

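### If the CRF holds one mean insulin dose per visit interval, the SAP's check for an insulin increase cannot apply the protocol's consecutive-day rescue criterion

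*Protocol*

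**What the plan says.** - **Rescue rule.** Protocol 4.3.3.1, in its guidelines on insulin dose, handles an up-titration of more than 10% as rescue medication when it is "lasting more than 7 consecutive days) in comparison to the mean daily insulin dose at baseline". Patients write down the daily dose, with a value on at least 80% of days, and review changes with the investigator. A patient who needs rescue is called within 5 days for the Week 24 procedures.
- **Dose summary.** Protocol 5.1.8 has the investigator calculate a mean from the diary: "The calculated mean daily insulin dose is an average daily insulin use from the last visit". The visit descriptions in protocol Section 4 repeat this task from Visit 3 onward.
- **SAP determination.** SAP 4.3.10 states that "the mean total insulin dose should be collected in the CRF which includes the dosing values with start and end dosing date". It fills missing doses or days by linear interpolation, and "The interpolated values will be used to determine if the increase" of at least 10% occurred. It gives no duration test.
- **Use in the analysis.** SAP 4.2.6.1 removes HbA1c measured after rescue medication or rescue insulin from the primary MMRM. SAP 4.3.2 limits HbA1c and FPG to values on or before the first rescue dose.
- **Other dose records.** Protocol 7.7 requires all medication in the eCRF, with dosages and dates of use. SAP 4.2.5.1 summarises rescue medication or insulin use from CRF records.

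**The concern.** The rescue rule has two parts, a size and a run of consecutive days. An average since the last visit keeps neither the run nor its date. The interval with the most averaging is also the one that ends at the primary time point.

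The primary estimand is the Week 24 difference without rescue. If an insulin increase that the protocol handles as rescue is not flagged, the HbA1c and FPG that follow it stay in the MMRM. If such increases are commoner on placebo, which is plausible but not stated, the retained values flatter placebo and shrink the treatment difference.

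Protocol 1.1 itself lists difficult capture of insulin dosing, and unmeasured differences in insulin adjustment between arms, among the limitations of the earlier renal study. This trial excludes rapid- and short-acting insulin, which reduces the problem. Long-acting, intermediate-acting and mixed insulins remain allowed, and insulin users form a randomization stratum.

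The point is separate from the difference between the protocol's threshold (more than 10%, more than 7 days) and the SAP's (at least 10%, no duration). Aligning the thresholds would still leave an interval mean unable to show consecutive days.

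**Working it through.** **1. The plan's own figure.** Protocol 8.2 gives a difference of 0.3, SD 0.9, two-sided 0.05 and 80% power. The normal approximation is n = 2(1.960 + 0.842)² × 0.9²/0.3² = 141.3, so 142 per group. With the noncentral t, power is 79.9% at 142 and 80.2% at 143, which reproduces 143. Then 143/0.95 = 150.5, so 151 per group and 302 in total. The sample size is not in dispute.

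**2. Interval lengths.** From protocol Table 1, the Week 12 to 24 interval is Day 169 − Day 85 = 84 days. Visits are scheduled "with a protocol-allowed visit window of ± 5 days", so it can run from 74 to 94 days. Week 4 to 12 is 85 − 29 = 56 days, and Week 1 to 4 is 29 − 8 = 21 days. The baseline mean, calculated at Visit 4, covers about the week since Visit 3.

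**3. Dilution.** Assume one mean per interval and a baseline dose on all other days. A rise of x% lasting d days in an interval of L days moves the mean by x × d / L percent. The duration needed to reach 10% is 10L/x days.

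For L = 84:

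| Rise | Days needed for the mean to reach +10% | Share of durations from 8 to 84 days that stay below 10% |
|---|---|---|
| 11% | 76.4 | 69/77 = 90% |
| 15% | 56 | 48/77 = 62% |
| 20% | 42 | 34/77 = 44% |
| 30% | 28 | 20/77 = 26% |
| 50% | 16.8 | 9/77 = 12% |

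The last column counts possible whole-day durations. It is not a forecast of how often episodes would be missed.

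- A 20% rise for 28 days gives 20 × 28/84 = 6.7%.
- Going from 50 to 60 units for the last 35 days gives (50 × 49 + 60 × 35)/84 = 54.2 units, or +8.3%.
- An 8-day rise must reach 10 × 84/8 = 105% (92.5% to 117.5% for 74 to 94 days). The same episode needs 70% in the 56-day interval and 26% in the 21-day interval.

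**4. The reverse error.** A 30% rise for 7 days within the 21-day interval moves the mean by 30 × 7/21 = 10%. That meets the SAP's threshold, although the protocol does not count 7 days as an up-titration.

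**5. Effect on the primary result, by assumption only.** The documents give neither the insulin share nor the rate of unrecorded up-titration. Bias = (insulin share) × (excess of missed episodes on placebo among insulin users) × (HbA1c lowering). Power is by noncentral t with 143 per group.

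- Insulin share 40%, excess 5 points, lowering 0.3: 0.40 × 0.05 × 0.3 = 0.006. The difference becomes 0.294 and power 78.6%.
- Insulin share 65%, excess 5 points, lowering 0.6: 0.65 × 0.05 × 0.6 = 0.0195. The difference becomes 0.2805 and power 74.7%.
- A harsher case, with an excess of 10% of all placebo patients and a lowering of 0.5: 0.10 × 0.5 = 0.05. The difference becomes 0.25 and power 64.8%.

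**The case against.** The interval mean may not be the only record that sets the rescue flag, and several parts of the documents support that.

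- **The site acts first.** Diaries are reviewed at each visit, changes can be discussed by telephone between visits, and rescue leads to a prompt visit and a CRF record. SAP 4.2.6.1 excludes values after rescue insulin without referring to 4.3.10. This stands: averaging matters only where the site does not identify and record the episode.
- **Dated doses may already be collected.** Protocol 7.7 asks for dosages and dates of all medication. The start and end dates in SAP 4.3.10 could describe dose segments, in which case the dilution shrinks or disappears. The SAP does not settle this, and its wording of a mean total dose matches protocol 5.1.8. The list of important deviations is blacked out. The amendment history mentions a criterion for insulin change over consecutive days, which hints at dated doses, but it concerns deviations rather than the rescue flag.
- **Interpolation.** A reader might infer that linear interpolation turns every step change into a ramp. The text does not support that, because it applies only to missing doses and date gaps.
- **Size.** Averaging hides mainly small or brief rises, so crediting them with an HbA1c effect as large as the planned difference is generous.
- **Other analyses.** The MI-RD and washout analyses use data regardless of rescue and do not depend on this flag. They target a different estimand, so they do not replace a correct flag in the primary analysis.

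**Conclusion.** The point holds in a conditional form. SAP 4.3.10 states a way of determining an insulin increase that cannot apply a consecutive-day criterion if the CRF holds one mean per visit interval. Over 84 days, a 20% rise lasting 8 to 41 days meets the protocol rule and stays below 10% in the mean. Such an episode is lost to the analysis only if the site does not record it as rescue. Neither document says which source governs when the site record and the derived flag disagree.

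Two stronger readings are not supported. One is that rescue insulin will be averaged away: the site route and the medication records may catch it. The other is that the primary result carries a bias of known size: every input to the bias figures comes from outside the documents. The effect is confined to insulin users with unrecorded increases and is probably small. It runs towards zero if up-titration is commoner on placebo, so this scenario raises no false-positive concern.

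The change is still worth making. The trial is powered at 80% for a difference of 0.3, and a failed primary test stops the secondary tests.

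**What to change.** 1. Reconcile protocol 4.3.3.1, 5.1.8 and 7.7 with SAP 4.3.10, so that one definition of an insulin increase applies and it is clear which insulin data the eCRF holds. Which definition to keep is for the sponsor.
2. In SAP 4.3.10, derive the insulin-rescue flag and date from dated dose changes treated as steps, using the dosages and dates that protocol 7.7 already requires, together with the rescue recorded by the site. State which source prevails if they disagree.
3. If the eCRF lacks dated insulin doses, add a dated yes/no item at each visit, completed from the diary, for an increase that meets the reconciled definition.
4. Use the since-last-visit mean for descriptive insulin summaries only.

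The cost is minor data entry for insulin users, some programming and a SAP wording change. No visits or samples are added.
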